2.2 Secondary estimands

Not applicable.

[figure not shown]
3 Study design

This is a randomized, parallel-group, open-label, multicenter study comparing an LDL-C management strategy including inclisiran plus usual care with usual care. A total of approximately 384 participants will be randomized 1:1 to aggressive LDL-C management with inclisiran plus usual care (intervention arm) and usual care (control arm). Identification of participants will take place during hospitalization or in the weeks following discharge with screening soon thereafter. Screening of participants must take place within 5 weeks after discharge.

Potential participants who are discharged after an ACS on statin therapy (which is considered routine care) or have documented statin intolerance will be screened and receive an LDL-C test

within 5 weeks post-discharge (to allow for the realization of the full effect of statin therapy). After the LDL-C test, participants with an LDL-C ≥70 mg/dL are eligible for the trial as long as they meet all other inclusion criteria. Participants will be randomized to inclisiran + usual care or usual care. All participants will be maintained on statin therapy during inclisiran treatment, but concomitant lipid-lowering therapy and LDL-C assessments will be at the discretion of the treating (primary) physician, mimicking real-world clinical decision-making and enabling the evaluation of inclisiran compared to usual care in patients with a recent ACS. Usual care may therefore include addition of ezetimibe, PCSK9-inhibiting monoclonal antibodies and/or commercially available inclisiran (Note: participants treated with inclisiran should not be treated with PCSK9-inhibiting monoclonal antibodies). After randomization, the treating physician will not have access to LDL-C values obtained as part of the study but will be able to perform LDL-C assessments at their discretion, to mimic usual care. The rationale of not providing the treating physician the LDL-C values obtained as part of the study is that those results might influence decisions made by him/her and could therefore undermine "usual care". Commercially available inclisiran may be used for appropriate patients in the usual care arm at the sole discretion of the treating physician, without any influence from the PI. LDL-C measurement and assessment of lipid lowering medications at each visit will be performed to assess adherence to background statin therapy.

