Women are considered post-menopausal and not of child bearing potential if they have had 12 months of natural (spontaneous) amenorrhea with an appropriate clinical profile (e.g., age appropriate, history of vasomotor symptoms) or have had surgical bilateral oophorectomy (with or without hysterectomy), total hysterectomy or tubal ligation at least six weeks ago. In the case of oophorectomy alone, only when the reproductive status of the woman has been confirmed by follow up hormone level assessment is she considered not of child bearing potential.

- 11. Treatment with other investigational products or devices within 30 days or five half-lives of the screening visit, whichever is longer.
 - a. Approved vaccines or vaccines used under Emergency Use Authorization should not be considered part of this exclusion criteria. Patients can receive COVID vaccines during inclisiran trials.
 - b. While use of COVID anti-viral therapies approved for use under Emergency Use Authorization would need to adhere to the washout period outlined above, prior to screening, they would not be considered as criteria for trial termination/discontinuation.
- 12. History of hypersensitivity to any of the study treatments or its excipients or to drugs of similar chemical classes.
- 13. Planned use of other investigational products or devices during the course of the study.
- 14. Any condition that according to the investigator could interfere with the conduct of the study, such as but not limited to:
 - a. Participants who are unable to communicate or to cooperate with the investigator.
 - b. Unable to understand the protocol requirements, instructions and study-related restrictions, the nature, scope, and possible consequences of the study (including participants whose cooperation is doubtful due to drug abuse or alcohol dependency).
 - c. Unlikely to comply with the protocol requirements, instructions, and study-related restrictions (e.g., uncooperative attitude, inability to return for follow-up visits, and improbability of completing the study).
 - d. Have any medical or surgical condition, which in the opinion of the investigator would put the participant at increased risk from participating in the study.
 - e. Persons directly involved in the conduct of the study.
- 15. Treatment with monoclonal antibodies directed towards PCSK9 or inclisiran within 90 days of screening.

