6.2.2 Prohibited medication

The treatments displayed in the table below are not allowed to be used simultaneously with inclisiran in the treatment arm. No modifications of therapy is required or recommended in the usual care arm.

Medication	Prohibition period	Action to be taken
Alirocumab (Praluent)	Participants randomized to inclisiran: monoclonal antibodies directed against PCSK9 are prohibited for the full duration of the study	Discontinue PCSK9 inhibitor
Evolocumab (Repatha)	Participants randomized to inclisiran: monoclonal antibodies directed against PCSK9 are prohibited for the full duration of the study	Discontinue PCSK9 inhibitor

Table 6-2 Prohibited medication

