intensity level to post-baseline lipid-lowering therapy addition group, and a shift table for statin intensity from baseline to Day 330/Last Visit will also be provided. To this end, the LLTs and statin intensity for Day 330/Last Visit will be assessed on the Day 330 visit date for participants with recorded Day 330 visit date, or on the study end date (date of last participation) otherwise. For the shift table for statin intensity from baseline to Day 330/Last Visit, the “None” category includes participants who did not take statin post baseline or who stopped the statin during the study.

Changes in LLTs prior to baseline will focus on statin and bempedoic acid taken within 30 days prior to study treatment start date, i.e. any time from day -30 to day -1. Number and percentage of participants will be presented for the following statin categories: initiation of statin therapy (no statin record present at day -30), discontinuation of statin therapy (no statin record present at day -1), increase in statin intensity, decrease in statin intensity, and change of statin within the same intensity group. Treatment gaps and/or overlapping treatment periods in case of two or more statins within the 30-day period will be ignored for analysis. If at least one statin record is present indicating that the statin was taken consistently on all days within the 30-day period, the participant will not be considered as having had any change in statin therapy.

For the analysis of lipid-lowering therapies at baseline a modified lipid-lowering therapy definition is also employed. For this analysis a modified lipid lowering therapy includes any statin, ezetimibe, PCSK9 inhibiting monoclonal antibodies, or bempedoic acid therapies.

The following medications will be included in the lipid-lowering therapy tables.

Table 2-3 Lipid-lowering Therapies

Medication	Medications included
Lipid Lowering Therapy	ATCCODE2=C10
Statin	ATCCODE2=C10 and CMDECOD contains ‘statin’, or ATCCODE4=C10AA, C10BA, or C10BX
Ezetimibe	ATCCODE2=C10 and CMDECOD contains ‘ezetimibe’
PCSK9 inhibiting monoclonal antibodies	ATCCODE2=C10 and CMDECOD contains ‘evolocumab’ or ‘alirocumab’
Bempedoic acid	ATCCODE2=C10 and CMDECOD contains ‘bempedoic acid’
Modified lipid lowering therapy	ATCCODE2=C10 and CMDECOD contains ‘statin’, ‘ezetimibe’, ‘evolocumab’, ‘alirocumab’, or ‘bempedoic acid’

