2.6 Analysis supporting secondary objectives

The secondary efficacy objectives include the following:

- To assess (1) the absolute change from baseline in LDL-C level by visit, and (2) average of percent and absolute changes from baseline in LDL-C levels to each post-baseline visit, in the inclisiran + usual care group compared to usual care group at Day 330
- To assess the proportion of participants reaching pre-specified LDL-C targets in the inclisiran + usual care group compared to usual care group at Day 330
- To assess plasma lipoproteins and triglycerides in the inclisiran + usual care group compared to usual care group at Day 330
- To assess changes in and adherence to background lipid-lowering therapy in the inclisiran + usual care group compared to usual care group at Day 330

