2.6.1 Secondary endpoint(s)

The secondary efficacy variables are the following:

1. Absolute change from baseline in LDL-C
2. Average percent change from baseline in LDL-C levels to each post-baseline visit
3. Average absolute change from baseline in LDL-C levels to each post-baseline visit

4. Achieving LDL-C < 100 mg/dL (yes, no) (among the subset of participants with LDL-C \geq 100 mg/dL at baseline)
5. Achieving \geq 50% reduction from baseline in LDL-C (yes, no)
6. Achieving LDL-C < 55 mg/dL (yes, no)
7. Percent change from baseline in apoB
8. Absolute change from baseline in apoB
9. Percent change from baseline in VLDL
10. Absolute change from baseline in VLDL
11. Percent change from baseline in non-HDL-C
12. Absolute change from baseline in non-HDL-C
13. Percent change from baseline in total cholesterol
14. Absolute change from baseline in total cholesterol
15. Percent change from baseline in Lp(a)
16. Absolute change from baseline in Lp(a)
17. Percent change from baseline in HDL-C
18. Absolute change from baseline in HDL-C
19. Percent change from baseline in triglycerides
20. Absolute change from baseline in triglycerides
21. Intensity of lipid-lowering therapy (decrease in dose, no change in dose, increase in dose)

Intensity of therapy is only available for statins, not for other lipid-lowering therapies used in this study. Therefore, for each participant and analysis visit, the highest statin intensity on each nominal visit date will be compared to baseline statin intensity. The decrease, no change, and increase in statin intensity at each visit will be assigned as follows:

Statin Intensity		Post-baseline Visit			
Baseline		High	Moderate	Low	None
	High	No change	Decrease	Decrease	Decrease
	Moderate	Increase	No change	Decrease	Decrease
	Low	Increase	Increase	No change	Decrease
	None	Increase	Increase	Increase	No change

22. Proportion of days covered (total number of days on either statin, ezetimibe, or PCSK9 inhibiting monoclonal antibody therapies divided by total number of study days)

If a participant did not take any of the three medications, then the total number of days will be assumed to be zero. Total number of study days is the total study duration (not treatment duration).

23. Discontinuation of statin therapy (i.e., no statin use \geq 30 days before the end-of-study visit) (yes, no)

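### Proportion of days covered (secondary variable 22) counts PCSK9-antibody days that only usual-care participants may accrue, so it needs a companion version limited to statin and ezetimibe days

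*SAP*

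**What the plan says.** SAP 2.6.1 defines variable 22 as the "total number of days on either statin, ezetimibe, or PCSK9 inhibiting monoclonal antibody therapies divided by total number of study days". A participant who took none of the three classes scores zero, and the denominator is the whole time on study. The same definition stands in Protocol Table 2-1 and Sections 8.3 and 12.5.1. Inclisiran days do not count in either arm.

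The objective it serves begins "To assess changes in and adherence to background lipid-lowering therapy in the inclisiran + usual care group" and sets that group against usual care at Day 330 (SAP 2.6).

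The antibody rule differs by arm. Protocol Table 6-2 reads "Participants randomized to inclisiran: monoclonal antibodies directed against PCSK9 are prohibited for the full duration of the study". For the control arm, Protocol 6.2.2 says "No modifications of therapy is required or recommended in the usual care arm", and Protocol Section 3 says "Usual care may therefore include addition of ezetimibe, PCSK9-inhibiting monoclonal antibodies and/or commercially available inclisiran". Exclusion criterion 15 (Protocol 5.2) rules out "Treatment with monoclonal antibodies directed towards PCSK9 or inclisiran within 90 days of screening".

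SAP 2.6.2 analyses variable 22 in the FAS by ANCOVA with treatment and baseline LDL-C, and reports a 95% confidence interval and a p-value. SAP 2.6.4 plans no sensitivity analyses of secondary variables. The supplementary analyses in SAP 2.6.5 cover variables 2 to 6 only.

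**The concern.** Randomization balances who would take a drug, but not who is allowed to. A usual-care participant who starts an antibody after stopping a statin goes on earning covered days. A participant on inclisiran who stops a statin and follows the protocol earns none, because the antibody is barred and inclisiran is not counted. The second participant has broken no rule and yet looks less adherent.

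The direction makes this harder to interpret. The sample-size sections (Protocol 12.8.1, SAP Section 3) already allow for less use of background therapy in the inclisiran arm. The definition moves variable 22 the same way, so a lower inclisiran value could not be assigned to behaviour or to the rule without further analysis.

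The exposure is concentrated. Participants with documented statin intolerance are eligible (Protocol 5.1, criterion 7). Variable 23 leaves them out (SAP 2.6.1); variable 22 does not. At stake is the reading of one secondary variable out of 23. Neither primary variable is affected.

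**Working it through.** **The plan's own figure.** There is none to reproduce. The documents give no expected value, standard deviation or power for variable 22, and no expected antibody uptake.

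**Step 1: which counted days each arm may accrue.**

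| Class | Counted in variable 22 | Inclisiran arm | Usual care |
|---|---|---|---|
| Statin | Yes | Allowed | Allowed |
| Ezetimibe | Yes | Allowed | Allowed |
| PCSK9 antibody | Yes | Prohibited throughout | Allowed |
| Inclisiran | No | Study treatment | Commercial product allowed |

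Only the antibody row is both counted and open to one arm.

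**Step 2: when an antibody day changes the result.** The definition reads most naturally as a union of days, although the SAP does not state that overlapping days count once. On that reading an antibody day adds to the numerator only if neither a statin nor ezetimibe was taken that day. Because of exclusion criterion 15, counted antibody days should come essentially from new starts after entry.

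**Step 3: size.** Let p be the mean covered proportion from statin and ezetimibe, taken as equal in both arms. Let

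- s = share of usual-care participants who start an antibody,
- f = fraction of study days on the antibody,
- u = fraction of those antibody days with no statin or ezetimibe.

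Then usual care has mean p + s × u × f, the inclisiran arm has mean p, and the excess in usual care is s × u × f. All three inputs are assumptions. With f = 0.75 and u = 0.25:

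- s = 2%: 0.02 × 0.25 × 0.75 = 0.00375, or 0.38 points
- s = 5%: 0.05 × 0.25 × 0.75 = 0.0094, or 0.94 points
- s = 10%: 0.10 × 0.25 × 0.75 = 0.0188, or 1.88 points
- any s with u = 0: 0 points

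**Step 4: effect on the test.** With 192 per arm (SAP Section 3), a two-sided 5% level (SAP 2.1) and an assumed SD of 0.25 or 0.35 for variable 22, the standard error of the difference is SD × √(2/192), that is 2.55 or 3.57 points. With equal statin and ezetimibe use, the chance of a nominally significant result is:

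| s (u = 0.25, f = 0.75) | SD 0.25 | SD 0.35 |
|---|---|---|
| 2% | 0.052 | 0.051 |
| 5% | 0.066 | 0.058 |
| 10% | 0.114 | 0.082 |

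**Step 5: after the change.** If only statin and ezetimibe days count, the antibody term is zero in both arms by construction.

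**The case against.** The best defence is that the objective covers changes in background therapy as well as adherence to it, and that the trial compares management strategies. Starting an antibody under usual care is such a change, and the bar on antibodies is part of the inclisiran strategy. On that view a difference in variable 22 is a real difference between strategies. No secondary estimand says otherwise, because SAP 1.2.2 sets none. This stands as a reason to keep the current definition. It does not help a reader who wants to know about adherence, which the objective also names.

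Second, the size is likely to be modest. Entry requires a statin or documented intolerance (Protocol 5.1). No change in lipid-lowering therapy is planned at screening (Protocol 4.1.1). Protocol 4.1 says that only a minority of eligible patients receive non-statin drugs, and antibody use without a statin or ezetimibe is a part of that minority. Two things work against the tilt: usual-care participants on commercial inclisiran also get no credit, and antibody days taken in the inclisiran arm against the rule would still count. This stands.

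Third, other outputs help. Variables 21 and 23 concern statins only, and SAP 2.4.2 tabulates concomitant lipid-lowering therapy by visit, with the antibodies as a separate class in Table 2-3. Those tables would show uptake, but they do not give a days-covered measure free of antibodies.

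A reader might also infer that leaving out bempedoic acid is part of the tilt, since SAP 2.4.2 says that "a modified lipid lowering therapy includes any statin, ezetimibe, PCSK9 inhibiting monoclonal antibodies, or bempedoic acid therapies". The documents do not support this. The drug is not on the prohibited list for either arm, so its omission does not follow from the prohibition, and that wider definition is set for the analysis of therapies at baseline.

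**Conclusion.** The asymmetry is in the text, and no planned analysis removes it. Part of any arm difference in variable 22 can come from the antibody prohibition, in the direction of higher coverage under usual care. Under the stated assumptions (2–10% uptake, a quarter of antibody days uncovered, antibody on 75% of study days) the tilt is about 0.4–1.9 points. That is less than one standard error of the difference at either assumed SD. It is zero if every antibody day is also a statin or ezetimibe day and overlapping days count once.

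A reader might infer a distortion of several points. The formula gives 7.5 points at 20% uptake with half the antibody days uncovered, but nothing in the documents supports inputs of that size. Nor do they show that variable 22 is invalid: as a description of the background drugs actually taken, it can be interpreted as it is. The point is a cheap improvement to one secondary analysis.

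**What to change.** Keep variable 22 as the protocol defines it; replacing it would alter a protocol-specified endpoint. Add to SAP 2.6.5 a supplementary version whose numerator is days on a statin and/or ezetimibe, the two counted classes open to both arms. Use the same denominator, the same ANCOVA and the FAS. State for both versions that a day covered by more than one drug counts once. State also that any conclusion about a difference in adherence rests on the supplementary version, with the protocol version read as a description of overall background drug use.

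The cost is one extra derivation and one table. The downside is that antibody days, which are real lipid-lowering treatment under usual care, do not count in the supplementary version, so the two results should be shown side by side. No treatment rule needs to change.

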Data collected at scheduled or unscheduled visits will be used in the analysis if they fall into an analysis window for an analysis visit. If more than one visit (scheduled or unscheduled) is made within the window specified above for any analysis visit, the non-missing assessment closest to the target study day will be used in the analysis for that visit. In the case of tied visits, non-missing data from the later visit will be used. In the case of identical collection dates and times, the average of the two visits will be used. However, all data will be included in the participant data listings.

Last Visit Summaries

The protocol uses the term End of Study (EOS) for Day 330. If a participant discontinues from the study early, they will have an early termination visit that is before Day 330. Using the windowing provided in [Table 2-2](#), the early termination visit will be assigned to the nearest analysis visit. Tables that summarize data by visit will include data by analysis visit (Baseline, Day 90, Day 270, and Day 330) along with a Day 330/Last Visit which will combine data from Day 330 for those participants who have data collected within the Day 330 analysis window with the data from the last post-baseline visit for those participants who do not have data collected in the Day 330 analysis window.

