2.5.6 Supplementary analyses

A supplementary analysis of primary efficacy variable 1 will be based on the following estimand:

- Population: Defined through appropriate inclusion/exclusion criteria to reflect the targeted population
- Variable: Percent change from baseline in LDL-C [The primary analysis time point is at Day 330.]

- Treatment: Inclisiran + usual care or usual care
- Remaining intercurrent events: 1. Potential use of inclisiran by participants in the usual care group. 2. Discontinuation of study treatment. 3. Use of prohibited medication (monoclonal antibodies directed against PCSK9, as defined in [Table 2-3](#)) in the inclisiran + usual care group. Data after the occurrence of either one of the above three intercurrent events will be excluded from the analysis (using MMRM).
- Summary measure: Least-squares mean difference between inclisiran + usual care group and usual care group

A supplementary analysis of primary efficacy variable 2 will be conducted by repeating the primary analysis based on observed LDL-C values per visit. Missing data will not be imputed. Therefore, the denominator for deriving the proportion of participants achieving LDL-C <70 mg/dL will be the number of participants with non-missing LDL-C per visit and treatment group.

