If a participant is considered a study completer and has a non-missing visit date for the nominal Day 330 visit recorded, a statin assessment date (to assess if the participant was taking statins at this point in time) will be calculated by subtracting 30 days from the Day 330 visit date (e.g., study Day 300 if the participant completes on study Day 330). The statin assessment date will be compared to the maximum statin end date of all statin medications taken by the participant. If the last statin is recorded as ongoing at study end date, the maximum statin end date will be set to the study end date.

If the participant was on a statin on or after this statin assessment day (maximum statin end date \geq statin assessment date), the participant will be considered as discontinued statin = 'no'.

If the participant was not on a statin on and after this statin assessment day (maximum statin end date $<$ statin assessment date), or they were a completer who did not have a Day 330 visit, the participant will be considered as discontinued statin = 'yes'.

All early termination participants will be considered to not be on a statin for this endpoint (the participant will be considered as discontinued statin = 'yes').

Participants who were not taking any statin while on study will be considered to not be on a statin for this endpoint (the participant will be considered as discontinued statin = 'yes').

The analysis will be based on the FAS excluding participants who had medical history of statin intolerance.

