2.6.3 Handling of missing values

For the analysis of secondary efficacy variables 1 and 7-20, the MMRM implicitly imputes missing data under a missing at random assumption.

For the analysis of secondary efficacy variables 4 – 6 and 23, participants with missing data will be imputed using “non-responder” (i.e., “negative” outcome) imputation.

For the analysis of secondary efficacy variables 2, 3, 21 and 22, missing data will not be imputed.

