2.6.4 Sensitivity analyses

Not applicable.

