2.6.5 Supplementary analyses

Secondary efficacy variables 2 and 3 will be analyzed using MMRM similar to the analysis of primary efficacy variable 1 and secondary efficacy variable 1, respectively. A linear combination of the estimated means will be used to estimate the time-adjusted percent change and absolute change from baseline in LDL-C, where “time-adjusted” refers to the estimated average from Day 90 through Day 330. Least-squares mean of each treatment group, least-squares mean treatment difference, 95% confidence interval for the treatment difference, and p-value based on the fitted model will be reported.

Secondary efficacy variables 4 – 6 will be analyzed similar to the supplementary analysis of primary efficacy variable 2 based on observed data only.

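### Statin discontinuation (secondary variable 23) counts every early leaver as having stopped, with no observed-data analysis beside it

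*SAP*

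**What the plan says.** Variable 23 asks whether the participant had stopped statins for at least 30 days before the end-of-study visit. SAP 2.6.1 compares the last statin date with a date 30 days before the Day 330 visit, and then sets two defaults:

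- Early leavers: "All early termination participants will be considered to not be on a statin for this endpoint".
- Completers also count as discontinued if they stopped in time "or they were a completer who did not have a Day 330 visit".

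Neither default consults the statin record. Participants with a history of statin intolerance are excluded from the analysis.

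The defaults belong to a wider rule. Protocol 12.5.1 prescribes negative-outcome imputation for variables 4–6 and 23. SAP 2.6.3 repeats it: for these variables, "participants with missing data will be imputed using" the non-responder rule. SAP 2.5.4 does the same for primary variable 2.

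The companion analyses differ:

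- Primary variable 2, SAP 2.5.6: "A supplementary analysis of primary efficacy variable 2 will be conducted by repeating the primary analysis based on observed LDL-C values per visit".
- Variables 4–6, SAP 2.6.5: they "will be analyzed similar to the supplementary analysis of primary efficacy variable 2 based on observed data only".
- Variable 23: not listed in 2.6.5, and 2.6.4 is marked not applicable.

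Elsewhere the SAP does use data from leavers. Under 2.1.1, "the early termination visit will be assigned to the nearest analysis visit", and Table 2-2 gives Day 330 a window of study Days 301 to 375. Under 2.4.2, statin intensity for Day 330/Last Visit is taken on the Day 330 visit date "or on the study end date (date of last participation) otherwise".

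**The concern.** Two things look wrong.

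First, the default overrides information that the SAP accepts elsewhere. Someone who leaves at study Day 310 with a statin recorded as ongoing can be an LDL-C responder at Day 330, be shown on a statin in the 2.4.2 shift table, and still count as having discontinued statins in variable 23.

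Second, and more important, variable 23 is the only non-responder-imputed endpoint visible in the public SAP without an observed-data companion. Its one estimate mixes two events. Equal dropout adds the same block of discontinuations to both arms and pulls the odds ratio towards 1. Unequal dropout can create or hide a difference.

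The endpoint is not incidental. Protocol 4.1 uses the effect on statin discontinuation as its example of why the trial is open-label, and gives detection of a meaningful difference in it as one reason for a one-year follow-up.

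**Working it through.** **Plan's own figures.** For a difference of 15, SD 40, two-sided alpha 0.025 and power 0.85: n per arm = 2 × (2.241 + 1.036)² × 40² / 15² = 152.8, so 153 per arm and 306 in total. Allowing for 20% loss, 153 / 0.80 = 191.25, so 192 per arm and 384 in total. Both agree with Protocol 12.8.1 and SAP section 3.

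**Inputs**
- Loss d = 20% at Day 330 (Protocol 12.8.1); 10% and 5% are shown as alternatives.
- About one-third of patients stop statins in three years (Protocol 4.1). At an assumed constant rate, q = 1 − (2/3)^(330/1095) = 0.115 by Day 330.
- n = 192 per arm. The number excluded for statin intolerance is not given, so this is an upper bound.
- Assumed for illustration: inclisiran halves q; dropout by arm; the share s of leavers who have truly stopped.

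**Who is coded as discontinued.** Coded rate = d + (1 − d)q; leaver share = d / coded rate.

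| Loss d | Coded rate | Leaver share |
|---|---|---|
| 20% | 0.200 + 0.800 × 0.115 = 0.292 (56 of 192) | 68% |
| 10% | 0.204 | 49% |
| 5% | 0.159 | 31% |

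**Dilution with equal dropout.** With q = 0.115 against 0.0575, the true OR is 0.061/0.130 = 0.47 if leavers behave like completers. At d = 20% the coded rates are 0.292 and 0.246, so the coded OR is 0.326/0.412 = 0.79 (0.70 at 10% loss, 0.62 at 5%).

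If a share s of leavers in both arms has truly stopped and the effect is confined to completers, each arm's true rate is ds + (1 − d)q. The true OR is then 0.72 at s = 50% and 0.76 at s = 75%, against the same 0.79 coded. Leavers wrongly coded number 34, 19 and 10 per arm for s = 11.5%, 50% and 75%.

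**Unequal dropout with no true effect.** At 25% (usual care) against 15% (inclisiran), the coded rates are 0.336 and 0.248, an OR of 0.65. The table gives the percentage of 400,000 simulated trials significant in favour of inclisiran, using an unadjusted Wald test on the log odds ratio at two-sided 0.05 (nominal 2.5% in that direction).

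| Dropout, usual care / inclisiran | 21% / 19% | 22.5% / 17.5% | 25% / 15% |
|---|---|---|---|
| Current rule | 6% | 16% | 48% |
| True status known, s = 50% | 4% | 7% | 15% |
| True status known, s = 75% | 5% | 11% | 30% |
| Observed data only | 2.4% | 2.3% | 2.4% |
| Recorded status, half of exits recorded | 4% | 7% | 17% |
| Recorded status, all exits recorded | 2% | 2% | 1% |

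The last three rows assume that leavers stop at the completers' rate. The recorded-status rows also assume uniform exit times, which gives a recorded stopping rate of 4.9% in leavers. The s = 50% and 75% rows show that part of the 48% would be a real difference if many leavers had stopped.

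**Power** (20% loss in both arms, q halved on inclisiran): current rule 17%, observed data 42%, recorded status 23% with half of exits recorded and 46% with all. If 10% are excluded for statin intolerance (173 per arm, assumed), the current rule has 16% power and gives 44% at 25%/15% dropout.

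**Overlap with the Day 330 window.** With 38.4 leavers per arm and uniform exits, 38.4 × 30/330 = 3.5 per arm leave in the last 30 days.

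**The case against.** The strongest reply is that the rule carries out the protocol. Protocol 12.5.1 prescribes negative-outcome imputation, the endpoint is tied to the end-of-study visit, and most early leavers have no such visit. That stands, and it is why the rule can remain the main analysis.

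Several further points also have force:

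- The conflict with recorded status near Day 330 affects only three or four leavers per arm if exits are uniform. The missing companion analysis is therefore the main gap.
- The documents predict neither unequal dropout nor a halving of discontinuation. The sample-size sections allow for lower use of background lipid-lowering therapy on inclisiran, which is the opposite direction. Dilution occurs either way, but the figures are illustrations, not forecasts.
- The added analyses have their own bias. With half of leavers stopped and the effect confined to completers, the true OR is 0.72; the current rule gives 0.79 and observed data 0.47. Even at 25% stopped (true OR 0.64), observed data is further from the truth.
- The secondary tests have no stated multiplicity control, so a significant result would carry limited confirmatory weight.

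Other planned outputs do not fill the gap. Variable 22 is formally tested without imputation over each participant's own time on study, but it pools statins with ezetimibe and PCSK9 antibodies. Variable 21 is not imputed, but it combines stopping with dose reduction. The shift table is descriptive. SAP 2.3.1 tabulates study discontinuation by arm but does not link it to variable 23.

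**Conclusion.** The point holds and is minor. At the planned 20% loss, roughly two-thirds of coded discontinuations would be leavers if completers stop at about 11.5%. How far that misleads depends on how many leavers have truly stopped, which a single imputed analysis cannot show. The odds ratio of 0.79 against 0.47 and the 48% figure are upper-end illustrations. They assume leavers behave like completers and, for the 48%, a ten-point dropout imbalance; at a two-point imbalance the figure is 6%. Neither primary analysis is affected. That variable 23 is the only such endpoint without a companion can be confirmed only for the visible text, since part of SAP 2.12 is blacked out.

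**What to change.** Keep the current rule as the main analysis if the sponsor prefers it, and add:

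1. **SAP 2.6.5:** include variable 23 in the observed-data analysis, defining observed as having a visit in the Day 330 window (study Days 301–375), early termination visits included.
2. **SAP 2.6.4:** a sensitivity analysis that takes status from recorded statin use in the 30 days before the study end date, the anchor already used in 2.4.2, and imputes discontinuation only where status at exit is unknown.
3. **Reporting:** show both beside early study discontinuation by arm, with the number of discontinuations that are imputed.

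The cost is SAP wording, two derived flags and two table rows, from data already collected.

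The limits should be stated. Status at exit covers less than 330 days and understates later stopping, and someone who leaves before Day 30 can hardly count as discontinued. Protocol section 8 makes the final visit depend on the participant's agreement, and those lost to follow-up are least likely to have a recorded status. Because the observed-data analysis can overstate an effect, the analyses should be read together, and none should replace the others.
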